Feasibility of recruitment: In 2019, 987 patients with OUD and CP diagnoses of back pain, arthritis, or neuropathy were hospitalized at Montefiore. Co-morbidities that would be exclusions for this RCT were: BUP treatment (7%), methadone treatment (31%), severe alcohol use disorder (8%), and severe benzodiazepine use disorder (2%). Removing patients with ≥ 1 exclusion leaves 640 potential participants. In a prior RCT of BUP treatment for hospitalized patients, 21% of eligible patients were enrolled.¹⁸ Using a more conservative estimate of enrolling 14% of eligible patients, enrolling 270 participants in 3 years will be feasible (640 eligible/year x 14% enrollment rate x 3 years = 270 participants).

D.2.5 Screening and Randomization: Initial screening and consent: Participants will be screened for eligibility and exclusion criteria by a trained research coordinator using a brief questionnaire. Participants will be informed of study procedures, risks and benefits of study participation, tested for their understanding, and they will provide written consent. During enrollment, female participants will have urine pregnancy tests.

Randomization will be unblinded, stratified, and blocked, with a 1:1 ratio across the two arms. To ensure balanced distribution between arms, we will stratify by OUD severity (misuse/mild vs. moderate/severe), heroin use (past 30 days, yes vs. no), and mood disorders (yes vs. no). We will randomize in blocks of 4-8 to ensure comparison groups of equal size. To ensure concealment of allocation, a centrally-located data manager will generate allocation sequences (with SAS Proc Plan) and store sequences in a password-protected file.

D.2.6 Participant tracking: We will use procedures that we have developed to retain people who use drugs in previous research, in which we have had an 84% retention rate over 6-month-follow-up.¹¹⁰ Participants will complete locator forms at enrollment and update them at all research visits. Information will include: 1) participants' addresses, phone numbers, and social security numbers; 2) contact information of family or friends; 3) contact information of participants' community-based organizations and case managers; and 4) participants' "hang out" locations.

Table E-2. Microdosing Initiation Dosing Schedule

Day	Microdosing			Standard Induction		
	Full agonist	BUP	Daily Total	Full agonist	BUP	Daily Total
1	Full dose	0.5 mg q12	1 mg	STOP	--	--
2	Full dose	1 mg q8	3 mg	--	2 mg q4 h	8 mg

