Other covariates: We will include covariates that may be associated with study outcomes including: sociodemographic characteristics (age, race/ethnicity, sex, employment, housing, insurance), opioid withdrawal and craving,^{111,125} adjunctive withdrawal medications (e.g., clonidine, loperamide), pain treatments including medications (e.g., NSAIDs, gabapentin) and other forms of treatment (e.g., physical therapy, steroid injections, surgery), mood symptoms (anxiety and depression),¹²⁶⁻¹²⁸ and prior OUD treatment. We will also include holistic outcome measures developed by the IMPOWR Coordination and Dissemination Center with people with lived experience (RFA-DA-21-029) and collaborate with the IMPOWR-ME Stakeholder Board to ensure we include other measures important to them.

D.2.11 Analytic plan Aims 1 and 2: Main analyses will be completed using an intention-to-treat approach.

[figure not shown]
Preliminary analyses. We will first review and summarize data using descriptive summaries and graphical analyses to ensure that values are within appropriate ranges, to check for outliers and abnormal values, and to verify that the distributions of measures meet the assumptions of the statistical tests that are planned as described below. We will also explore whether the microdosing and TAU groups are equivalent on potential confounding variables (age, sex, race/ethnicity, baseline substance use, and mood symptoms).

Missing data. For missing data, we will use multivariate multiple imputation using the fully conditional specification method.¹²⁹ We will repeat imputations five times, and then we will compare statistical results using datasets that include imputed values and the dataset that drops missing values. This will guide interpretation of our assessment of the impact of missing data, as well as, our interpretation of overall results.

Aim 1: To test the effectiveness of microdosing (vs. TAU) on OUD outcomes.

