microdosing (nearly 100%), we will use a more conservative estimate of treatment uptake from our experience with microdosing (61%). In a controlled trial of standard induction to transition patients with CP from full opioid agonists to BUP, only 24% were successful with BUP uptake.⁵⁸ To detect a difference of this size in BUP uptake, we would only need 27 participants in each arm to assure 80% power. However, we will recruit a larger sample to account for the possibility that uptake will be greater than 24% in the TAU arm (see **Table E-5**). Even with study attrition, we will be

able to assess BUP uptake for all participants based on medical record extraction,

For pain outcomes, we based our power calculations on expected changes in pain intensity from baseline to 3 months. Our pilot data (see D.1.1) suggests that mean (SD) pain intensity score will be 7.3 (± 1.6) at baseline for all participants. With a sample of 270 participants (135 per arm), the minimum effect size (Cohen's d) that can be detected with power of 80% is 0.34. This effect size corresponds to a difference between arms (microdosing vs. TAU) of 8.4% for participants'

reduction in pain scores (assuming that the SD of change is 1.8). Note that the SD for the pain score change is greater than that of the pain intensity score at each time point due to the intra-participant correlation in pain intensity over time. Because pain reduction is only considered for participants with BUP uptake, attrition is already incorporated into these estimates.

D.3 Aim 3a) Examine factors influencing reach, adoption, implementation, and maintenance of the microdosing protocol.

D.3.1 Overview and hypotheses. In this hybrid type 1 effectiveness-implementation trial, we will use RE-AIM and CFIR frameworks to guide Aim 3a, in which we will use qualitative and quantitative methods to describe multi-level factors influencing reach, adoption, implementation, and maintenance of BUP microdosing.

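### Five imputations are valid but leave avoidable seed-to-seed noise in the imputed results for the visit-based secondary outcomes; 50 would cut its SD by 68% for computing time alone.

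*Combined protocol and SAP*

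**What the plan says.** Section D.2.11 (Missing data) plans "multivariate multiple imputation using the fully conditional specification method" and continues "We will repeat imputations five times". The natural reading is five imputed datasets. The team will then "compare statistical results using datasets that include imputed values and the dataset that drops missing values", and this comparison is meant to inform both the judgement on missing data and the reading of the overall results.

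The section gives no reason for five, no seed, no pooling rule, no expected missing fraction and no target for Monte Carlo error. It does not say whether the imputed or the complete-case result is the main one.

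The only guide to how much may be missing is section D.2.6, which says of the group's earlier research: "we have had an 84% retention rate over 6-month-follow-up". Section D.2.12 states that the primary outcome can be obtained from the medical record for every participant. The key-outcomes section (headed E.2.10) defines BUP retention by prescriptions written, so little of it should need imputing.

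**The concern.** With a small number of imputations, the pooled estimate and its p-value depend partly on the random numbers drawn. The usual defence of five is that little average efficiency is lost. That is true, but it does not limit how far one reported p-value can move between seeds.

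Two things are at stake. First, a visit-based secondary result close to a significance threshold could fall on either side of it for no reason in the data. Second, the plan uses the gap between imputed and complete-case results as evidence about missing data, and noise from the imputation draws adds to that gap.

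**Working it through.** **Inputs from the documents.** m = 5 (D.2.11); 135 per arm, detectable d = 0.34 at 80% power, SD of change 1.8, baseline pain mean 7.3 and SD 1.6 (D.2.12); 84% six-month retention in earlier research (D.2.6).

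**Assumptions.** The fraction of missing information (FMI) is not given. I use 0.05 to 0.30, with 0.16 = 1 − 0.84 as a middle value. Two-sided alpha of 0.05 is assumed, since the plan states none.

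**The plan's own figure.** There is no calculation behind the five imputations to reproduce. The power figure for pain does reproduce: d = (1.960 + 0.842) × √(2/135) = 0.341, against 0.34 stated. Also 0.34 × 1.8 = 0.612 points, and 0.612/7.3 = 8.4%, as stated.

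**Monte Carlo SD of the pooled estimate, in standard errors: √(FMI/m).**

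| FMI | m = 5 | m = 50 |
|---|---|---|
| 0.05 | 0.100 | 0.032 |
| 0.16 | 0.179 | 0.057 |
| 0.30 | 0.245 | 0.077 |

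Whatever the FMI, the ratio is √(5/50) = 0.316. The SD falls by 68% and the variance by 90%.

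**Spread of the reported p-value when the noise-free z is 1.96.** The range is z = 1.96 ± 1.96 × √(FMI/m), converted to two-sided p.

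| FMI | m = 5 | m = 50 |
|---|---|---|
| 0.05 | z 1.76 to 2.16, p 0.078 to 0.031 | z 1.90 to 2.02, p 0.058 to 0.043 |
| 0.16 | z 1.61 to 2.31, p 0.108 to 0.021 | z 1.85 to 2.07, p 0.064 to 0.038 |
| 0.30 | z 1.48 to 2.44, p 0.139 to 0.015 | z 1.81 to 2.11, p 0.071 to 0.035 |

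**Average efficiency.** Relative efficiency is 1/(1 + FMI/m). At FMI 0.16 this is 0.969 with m = 5 and 0.997 with m = 50. The SE with m = 5 is √(1 + 0.16/5) = 1.016 times its value with unlimited imputations, so the average loss is small.

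**Simulation check.** Set-up: 135 per arm, SD 1.6, correlation 0.37 (which gives an SD of change of 1.8), an assumed true difference of 0.45 points, outcomes missing completely at random, regression imputation and ANCOVA, with 60 datasets and 60 seeds each. At 16% missing the Monte Carlo SD was 0.174 SE with m = 5 and 0.056 with m = 50, in line with the formula. Two seeds disagreed on p < 0.05 in 8.6% of pairs with m = 5 and 1.7% with m = 50. At 30% missing the figures were 15.2% and 2.9%. With 60 datasets these percentages are rough.

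**Away from the threshold.** The 0.45-point difference gives an expected z of about 0.45/0.199 = 2.3, close to the threshold. At the planned effect, z is about 0.612/0.199 = 3.1, where 0.199 is the simulated SE. Let q be the chance that a seed gives |z| > 1.96, and average 2q(1 − q) over sampling variation at FMI 0.16. Two seeds then disagree in about 4% of pairs with m = 5 and 1.3% with m = 50. With no true effect the figures are about 2.5% and 0.8%.

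**The imputed versus complete-case comparison.** Suppose only the outcome is missing and the imputation model holds just the analysis variables. The imputed estimate then converges on the complete-case estimate as m grows. In that case the gap seen with m = 5, about 0.18 SE at FMI 0.16, is essentially all Monte Carlo noise.

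**The case against.** The strongest reply is that five imputations are not an error. Rubin's rules carry the finite number of imputations into the standard error through the (1 + 1/m) term, and no bias or inflation of type I error has been shown. This stands: the gain is in precision and stability, not validity.

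A reader might infer that all secondary results depend on the seed. The documents do not support that. BUP retention comes from prescriptions, the complete-case results involve no seed, and the mixed-effects models planned for illicit use and pain can use incomplete follow-up without imputation. The point is limited to the imputed results for visit-based outcomes and to the comparison that uses them.

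A reader might also take 0.16 as an upper limit on the FMI. It is not. The 84% comes from other research, so loss in this hospitalized cohort could be higher. The main pain analyses end at 3 months, so loss could also be lower. The proportion missing is not the same as the FMI, and good auxiliary variables would reduce it. One further simulation, with an earlier visit added at an assumed correlation of 0.6, lowered the m = 5 noise only from 0.18 to 0.15 SE.

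It is fair to say that conclusions would change on re-running the same code only if no seed were set. The plan is silent on seeds; it does not say that runs will be unseeded. It is also fair that 50 is not a unique answer: at FMI 0.16, 20 imputations would already halve the SD (0.089 against 0.179).

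**Conclusion.** The point holds as a minor, nearly free improvement. Five imputations leave seed-to-seed noise of 0.10 to 0.24 SE in the pooled estimates for pain intensity, pain interference, quality of life, self-reported illicit opioid days and urine tests, over an assumed FMI of 0.05 to 0.30. With 50 it is 0.03 to 0.08 SE. The consequence is confined mainly to results near a threshold, and the plan names no alpha for these outcomes. Across all results at the planned pain effect, the gain is a few percentage points in agreement between seeds.

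The planned inference is not invalid, and the primary outcome is not at risk. The separate question of whether the imputed or the complete-case result is the main one stays open whatever the number of imputations.

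**What to change.** In D.2.11, replace five imputations with 50 and state that the random seed will be fixed and recorded before analysis. The two parts do different work: the seed makes the result reproducible but leaves its Monte Carlo error unchanged, while the larger number reduces that error. No participants, data collection or design change is needed. The cost is computing time, somewhat more for the structural equation models that use the EMA data.

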Secondary OUD outcomes include illicit opioid use and BUP retention. **Illicit opioid use** will be examined as the number of days of illicit opioid use (defined as self-reported use of heroin, fentanyl, or non-prescribed opioid analgesics) in the prior 30 days based on the Addiction Severity Index (continuous).¹¹⁹ Because urine drug testing (UDT) only captures opioid use in the prior 24-72 hours, it is a less sensitive measure of substance use over time; however, UDT results will be a secondary outcome measure. **BUP retention** will be

Table E-4. Ecological Momentary Assessment (EMA) Measures

Construct	Measure
EMA opioid- and pain-related symptoms	
Opioid withdrawal	Subjective Opioid Withdrawal Scale (SOWS)
Opioid craving	Visual analog scale
Pain intensity	Adapted BPI pain severity subscale
Anxiety	Generalized Anxiety Disorder-7 (GAD-7)
Exploratory EMA outcomes	
Illicit opioid use	Self-report
BUP dose	Self-report
Pain treatment	Self-report

*All measures will occur at bursts 1 & 2 weeks, and 1, 2, & 3 months

defined as having a BUP prescription written the following number of days after baseline: 30-60 days (1-month retention); 90-120 days (3-month retention); and 180-210 days (6-month retention). To be retained at 3 and 6-months, participants will be required to have been retained at previous time points.⁴⁶ All OUD outcomes are consistent with elements of the Opioid Use Disorder Cascade of Care.¹²⁰

Secondary pain outcomes include pain intensity, pain interference, and quality of life. *Pain intensity* will be measured using the Brief Pain Inventory (BPI).¹²¹ We will use the mean of 4 items that assess pain intensity over the past 24 hours on a scale of 1-10 (1=minimal pain, 10=intense pain). We will use the mean of these 4 items. *Pain interference* will be measured using the pain interference scale from the BPI, which is a 7-item instrument measuring the impact of pain on daily activities and physical functioning. It is rated on a scale of 1-10 (1=minimal interference, 10=high interference). We will use the mean of these 7 items. *Quality of life* will be measured using the PROMIS-Preference Scoring System (PROP-Pr), which is described in detail as part of the cost-effectiveness analyses below (see D.4.1).¹²²⁻¹²⁴ In our main analyses, we will examine changes from baseline to 3 months for all pain outcomes; in additional analyses, we will examine sustainability at 6 months.

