H₁: *The microdosing arm (vs. TAU) will have better BUP treatment uptake and retention, and less illicit opioid use.* Our primary analysis will be a logistic regression comparing the proportion of participants in each study arm who meet our definition of BUP uptake (see D.2.10). Secondary analyses will examine BUP retention and illicit opioid use as secondary outcomes. We will use a mixed effects logistic regression model to examine BUP retention at 1, 3, and 6 months and a mixed effects linear regression model to examine number of days of illicit opioid use (over 30 days) at 1, 3, and 6 months. Study arm will be considered a fixed effect, and participant and time (months) will be considered random effects. Additional analyses will include key variables mentioned above as covariates and potential confounders if they differ by study arm.

H₂: *Improvements in H₁ will be mediated by opioid- and pain-related symptoms.* Based on the model

described in **Figure E-3**, we will use structural equation modeling to determine whether improvements in OUD outcomes are due to improvements in opioid- and pain-related symptoms. We will use EMA data (5 random reports per day) and data from in-person visits at baseline, 1 week, 1, 3, and 6 months. For example, when the dependent variable is BUP uptake, we will calculate the standardized total effect from the intervention (BUP microdosing) to BUP uptake, as well as the standardized mediational (i.e., indirect) effect of opioid- and pain-related symptoms (e.g., withdrawal). The mediational effect is calculated as the product of the effect from intervention to the mediator, and the effect from the mediator to the outcome. To account for the influence of the baseline measures (e.g., sociodemographic characteristics) on the outcome and the mediator, we will use a partial correlation matrix as the input matrix. This will be created by statistically parsing out the effects of the baseline measures cited above on the mediator and the outcome variable. Our proposed model will be estimated using Mplus.¹³⁰ Overall model fit will be assessed by: (1) the root mean

[figure not shown]

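### Agreement between imputed and complete-case results cannot rule out loss that depends on unseen opioid use, and no other missing-data check is planned for self-reported illicit use

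*Combined protocol and SAP*

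**What the plan says.** In the combined protocol and SAP, D.2.11 (Missing data) states that "we will use multivariate multiple imputation using the fully conditional specification method" and that "We will repeat imputations five times". The check is a comparison: "we will compare statistical results using datasets that include imputed values and the dataset that drops missing values". Its purpose is stated too: "This will guide interpretation of our assessment of the impact of missing data", and of the overall results as well. The variables in the imputation model are not listed. It is also not said whether missing values are dropped by visit or by participant.

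The outcome most exposed is illicit opioid use. The key-outcomes section (numbered E.2.10) counts days in the prior 30 from "self-reported use of heroin, fentanyl, or non-prescribed opioid analgesics", and adds that "UDT results will be a secondary outcome measure". Under H1 in D.2.11 the analysis is "a mixed effects linear regression model to examine number of days of illicit opioid use (over 30 days) at 1, 3, and 6 months". No rule is given for a missing urine test.

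No attrition rate is stated for this trial. The nearest figure is in D.2.6, where the group reports for its previous research that "we have had an 84% retention rate over 6-month-follow-up".

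**The concern.** A participant who cannot be reached contributes no days of use at that visit, and in this population heavier use is a plausible reason for being out of reach. Standard multiple imputation fills the gap from people who were seen and who look similar on the recorded variables. Complete-case analysis leaves the gap out. Neither lets the lost participants differ from the observed ones in ways the data do not show, and the planned mixed models do not either. If such a difference exists, the two results can sit close together and both be wrong.

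The plan makes this comparison its guide to the impact of missing data. It contains no delta-adjusted, tipping-point or missing-equals-use analysis. At stake is the size, and possibly the direction, of the arm difference in illicit use, which is one of the three outcomes named in H1.

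**Working it through.** The plan gives no figure for the effect of missing data, so there is none to reproduce.

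**Inputs from the documents.** 135 per arm (D.2.12). Retention of 84% in earlier research (D.2.6) implies 100% − 84% = 16% loss, or 0.16 × 270 ≈ 43 participants. This is a 6-month figure from other studies, used here as a stand-in.

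**Assumed inputs (not in the documents).** SD of days of use 9; excess use among those lost 5 to 10 days per 30; the splits of loss by arm; the strength of the predictors. The simulations use normal values and ignore the limits of 0 and 30.

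**Step 1: no useful predictors.** The observed mean in an arm is too low by loss × excess. For the difference, microdosing minus TAU (negative favours microdosing):

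bias = loss(TAU) × excess(TAU) − loss(micro) × excess(micro)

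| Loss TAU / micro | Excess TAU / micro (days) | Bias (days) |
|---|---|---|
| 16% / 16% | 10 / 10 | 1.6 − 1.6 = 0 |
| 20% / 12% | 10 / 10 | 2.0 − 1.2 = +0.8 |
| 24% / 8% | 10 / 10 | 2.4 − 0.8 = +1.6 |
| 24% / 8% | 5 / 5 | 1.2 − 0.4 = +0.8 |
| 16% / 16% | 10 / 5 | 1.6 − 0.8 = +0.8 |
| 12% / 20% | 10 / 10 | 1.2 − 2.0 = −0.8 |

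A positive bias shrinks a true benefit of microdosing; a negative one inflates it. With equal loss and equal excess the difference is unbiased, although each arm's mean is still 1.6 days too low.

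**Step 2: how far imputation repairs this.** Suppose a recorded predictor has correlation ρ with days of use among those observed, and the lost participants' excess shows in it to the same degree. Regression imputation then recovers ρ² of the excess, so its bias is (1 − ρ²) times the complete-case bias. For 20% versus 12% loss and 10 days of excess:

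- ρ = 0: complete case 0.80, imputed 0.80
- ρ = 0.4: complete case 0.80, imputed 0.84 × 0.80 = 0.67
- ρ = 0.9: complete case 0.80, imputed 0.19 × 0.80 = 0.15

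A simulation of 4,000 trials per setting (135 per arm, five imputations) gave the same values to two decimals. At ρ = 0.4 the two estimates differed by 0.25 day on average. The standard error of the complete-case difference is about 9 × √(1/108 + 1/118.8) = 1.2 days, so a reader would see agreement.

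**Step 3: a different mechanism.** In a second simulation the chance of loss rises directly with the unseen days of use, the predictor correlation is 0.4, and TAU loses more (23% versus 9%). The full-data difference was −3.01 days, complete case −1.63 and imputed −1.84. With no true effect and loss of 21% versus 11%, the complete-case difference was +0.97 and the imputed one +0.84.

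**Step 4: what the planned check can show.** When loss of 21% versus 11% depended only on the observed predictor, the full-data difference was −3.04, complete case −2.66 and imputed −3.06. Here the two diverge and imputation is right. The comparison therefore responds to loss related to observed data, but says little about loss related to unseen use.

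**The case against.** The strongest reply is that the two analyses need not be biased alike. The plan collects much that could predict use: ASI and urine tests at every study visit, EMA reports of illicit use through 3 months, and prescription records that need no visit. If these enter the imputation model and predict well, imputation removes most of the bias and moves away from the complete-case result, as Step 2 shows at ρ = 0.9. This stands as a limit on the point. It does not dispose of it, because the plan does not say which variables enter.

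It is also fair that the documents give no evidence on the excess, the split of loss by arm, or whether loss is driven by use. The protocol works against loss with locator forms, paid visits and questionnaires that can be completed virtually. At 0.8 day the bias is below one standard error of the difference. These facts limit the likely size; they do not make the check informative about unseen use.

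Three stronger readings are tempting and are not supported:

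- A reader might infer that the complete-case comparison is useless. Step 4 shows that it can reveal loss related to observed data.
- A reader might infer that the trial is tilted towards microdosing. The direction depends on which arm loses more; greater loss in TAU works against microdosing.
- A reader might infer that the main result is in doubt. Uptake comes from EHR data, and D.2.12 says it can be assessed for every participant. Retention is prescription-based. What remains there is care outside the system, which D.5 acknowledges.

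**Conclusion.** The point holds for self-reported days of illicit opioid use, a secondary outcome. Agreement between imputed and complete-case results would not show that the arm difference is robust to loss driven by unseen use, and the plan has no other analysis that addresses it.

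With SD 9, a 10-day excess, 16% overall loss and no useful predictors, the difference is off by about 0.8 day at 20% versus 12% loss and 1.6 days at 24% versus 8%. At a predictor correlation of 0.4, imputation would still carry 0.67 of the 0.8 day; at 0.9, only 0.15. The bias is about zero if loss and excess are equal across arms. All of these sizes rest on assumed inputs and show scale only. The documents do not establish that loss will be unequal or use-driven.

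This is a worthwhile improvement and not a threat to the primary conclusion.

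**What to change.** 1. Keep multiple imputation as the main analysis, and name its variables: arm, earlier visits, urine tests, EMA reports and EHR prescription data.
2. Keep the complete-case result as a descriptive comparison.
3. Add a delta-adjusted imputation of days of illicit use. Add a shift to the imputed values, varied separately by arm (for example 0, 5, 10 and 15 days), with shifted values capped at 30. Report the combinations at which the conclusion changes.
4. Base the statement on robustness to missing data for this outcome on step 3.

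Fix these choices before outcome data are examined. No new data are needed. The cost is a few extra runs of the same imputation model and possibly a more cautious conclusion on this secondary outcome. The shift values are illustrative, since the documents offer no source for them; the team should choose a range it finds plausible.
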